## **2. Intervention measures**

2.1 Control group: Conventional treatment methods were adopted, including surgery, drug therapy, nutritional support, Chinese medicine, and acupuncture, as well as prevention of complications. Meanwhile, median nerve electrostimulation (Shenzhen Dongdi Xin Technology Co., Ltd, MT1023 multifunctional electrotherapy comprehensive treatment instrument) was combined, with two treatments per day (skin electrodes were placed 2cm above the wrist transversease on the anterior aspect of the right forearm, using direct current asymmetric rectangular wave, stimulation intensity of 20mA, pulse width of 300ms, frequency 40Hz, working for 20 seconds per minute, resting for 40 seconds, generally lasting for 60 minutes, and lasting for about 8 weeks.

2.2 Experimental group: In addition to conventional rehabilitation treatment methods and median nerve electrostimulation, auricular acupuncture was combined, with acupuncture at heart, Shenmen, sympathetic, and subcortical points (Suzhou Medical Supplies Co., Ltd., Hua Tuo brand disposable sterile push acupuncture model 0.20×0.8mm).

The family members were instructed to massage each acupoint three times a day, each time for 10 minutes with moderate pressure, each treatment for 3 days, rest for 1 day, repeat three times, a total of 11 days in one course of treatment.

### **3. Observation indicators**

After 4, 6, and 8 weeks of continuous intervention, the awakening conditions, including GCS, GOS outcome evaluation, CRS-R scores, and family satisfaction, were compared.

3.1 Awakening conditions: The time of patient awakening and the awakening at 4, 6, and 8 weeks after intervention were recorded.

3.2 The GCS scale (Glasgow Coma Scale) includes three dimensions: opening, language, and motor, with a full score of 15 points. The lower the score, the worse the patient's neurological function recovery.

3.3 CRS-R (Coma Recovery Scale-Revised): It adds evaluation content such as arousal response, communication ability, and auditory level compared to the GCS scale. lowest score is 0, and the highest score is 23. The higher the score, the higher the level of consciousness.

3.4 Prognosis evaluation was at 1 month after treatment based on the Glasgow Outcome Scale (GOS). A score of 5 indicates good recovery, 4 indicates moderate disability, 3 indicates disability, 2 indicates a vegetative state, and 1 indicates death.

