##### **1.1 Inclusion criteria**

- ① All patients with disturbance of consciousness after brain injury;
- ② Stable vital signs no obvious bleeding, GCS score of 4-8 points;
- ③ No severe organ failure, normal heart function;
- ④ Course of disease within 10 days
- ⑤ No history of head injury, no history of pregnancy and epilepsy.

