#### **4.Statistical treatment**

SPSS27.0 statistical software was used for analysis, and the count data of each group was expressed as percentage or composition ratio. The X test was used for the percentage or composition ratio between groups. The measurement data of each group was expressed as mean ± standard deviation (x̄-s). Comparison within the group before and after treatment and comparison between the two groups were performed by t-test. P<0.05 was considered statistically significant.

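### No baseline CRS-R assessment is scheduled, although a before-and-after comparison is planned; the only pre-treatment score is the eligibility GCS

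*Combined protocol and SAP*

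**What the plan says.** In the combined protocol and SAP, section 3 (Observation indicators) opens with the timing of the comparisons: "After 4, 6, and 8 weeks of continuous intervention, the awakening conditions, including GCS, GOS outcome evaluation, CRS-R scores", with family satisfaction completing the list. Item 3.3 describes CRS-R by its range ("lowest score is 0, and the highest score is 23") and gives it no assessment time of its own. Item 3.1 adds the awakening record: "The time of patient awakening and the awakening at 4, 6, and 8 weeks after intervention were recorded". Item 3.4 places the GOS evaluation one month after treatment.

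Section 4 (Statistical treatment) states for measurement data: "Comparison within the group before and after treatment and comparison between the two groups were performed by t-test". It names neither the scores that enter the before-and-after test nor the time that counts as before.

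The one score that must exist before treatment comes from section 1.1 (Inclusion criteria): "Stable vital signs no obvious bleeding, GCS score of 4-8 points". That section does not say when this GCS is taken relative to randomisation or first treatment. Patients may enter up to 10 days into the course of the disease.

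**The concern.** The analysis section presupposes a starting value that the assessment section does not order. GCS and CRS-R are the plan's two scales of level of consciousness. The plan itself presents CRS-R as adding content to GCS. For CRS-R, staff who follow section 3 exactly would take the first score at week 4. An analyst cannot repair this later, because the patient's state at entry has passed.

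Three things are at stake:

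- the within-group before-and-after test for CRS-R;
- the ability to describe how similar the arms were on CRS-R at entry;
- the precision that a baseline covariate would give the between-arm comparison in a trial of 60 patients.

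A smaller consequence concerns section 1.3, under which a patient whose participation is stopped is analysed on the last available result. A patient stopped before week 4 has no scheduled CRS-R result to use.

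**Working it through.** **Cross-check of schedule against analysis.** The plan states no figure to reproduce here, so the first step is to set the sections side by side.

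| Measure | Scheduled before treatment | Scheduled later |
|---|---|---|
| GCS | Implied by eligibility (4 to 8), timing not fixed | 4, 6, 8 weeks |
| CRS-R | None | 4, 6, 8 weeks |
| GOS | None (an outcome scale) | 4, 6, 8 weeks in the opening sentence; 1 month after treatment in item 3.4 |
| Family satisfaction | None | 4, 6, 8 weeks |

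The absence of a before value is natural for GOS and satisfaction. GCS has a value of uncertain timing, limited to five possible scores (8 − 4 + 1 = 5). CRS-R is the consciousness scale with nothing scheduled.

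**Chance imbalance that would go unseen.** Input: 30 patients per arm (section 1, Subjects). Work in units of the baseline SD and use the normal approximation.

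- SE of the difference in baseline means = √(1/30 + 1/30) = √(2/30) = 0.258 SD.
- P(|difference| > 0.3 SD): z = 0.3/0.258 = 1.16, two-sided probability 0.245.
- P(|difference| > 0.5 SD): z = 0.5/0.258 = 1.94, two-sided probability 0.053.

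These figures describe ordinary sampling variation under randomisation. They show how often a noticeable imbalance would exist without being recorded. They are not a measure of bias.

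**Precision forgone.** Let r be the correlation between baseline and follow-up CRS-R. The documents give no value, so the range 0.3 to 0.7 is an assumption. With equal SDs at both times, and relative to analysing the follow-up score alone:

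- ANCOVA variance = 1 − r² (ignoring the small cost of estimating the slope);
- change-score variance = 2(1 − r);
- equivalent number per arm under ANCOVA = 30/(1 − r²).

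| r | ANCOVA variance | Variance removed | Equivalent per arm | Change-score variance |
|---|---|---|---|---|
| 0.3 | 0.91 | 9% | 33 | 1.4 |
| 0.5 | 0.75 | 25% | 40 | 1.0 |
| 0.7 | 0.51 | 49% | 59 | 0.6 |

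The way the baseline is used matters. A change-score t-test is less precise than ignoring the baseline when r is below 0.5 (40% more variance at r = 0.3). ANCOVA is at least as good as either across this range.

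**The case against.** The strongest reply is that the gap is one of writing. The opening sentence of section 3 says when indicators are compared, which is not necessarily a complete calendar of assessments. Section 4 implies that some before measurement exists, and nothing forbids a CRS-R at entry. This stands to the extent that intent cannot be judged from the text. It does not remove the problem: staff work from the schedule, and the schedule does not order the score.

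A reader might go further than the documents allow in three ways.

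- *That every score is taken only at 4, 6 and 8 weeks.* This is not so. GCS must be scored for entry, and item 3.4 sets GOS at one month after treatment.
- *That the before-and-after comparison of CRS-R is impossible.* The text is silent on a baseline CRS-R; it does not exclude one. Section 4 also does not name CRS-R as a before-and-after measure, and entry GCS could supply one such test.
- *That a CRS-R difference between arms at week 4 cannot be told apart from a difference present at entry, so the comparison is biased.* Patients are randomised. Chance imbalance at entry is already part of the sampling error of the follow-up t-tests and adds nothing to their nominal 5% error rate. The entry GCS also gives a partial check of balance.

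Two further points stand. The within-group test does not compare the arms, so losing it does not remove the estimate of the treatment effect. And restricting entry to GCS 4 to 8 may narrow the spread of CRS-R at entry and pull r towards the low end of the assumed range.

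**Conclusion.** The omission is real and worth correcting before patients are enrolled. As scheduled, the planned before-and-after test is not supported for CRS-R, and neither baseline adjustment nor a check of CRS-R balance at entry is possible. Taking the random allocation as sound, the between-arm comparisons at 4, 6 and 8 weeks stay valid; the loss there is in precision and description.

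The loss of precision runs from modest to substantial, depending wholly on the assumed correlation. At the lower end it is worth about 3 patients per arm (33 against 30), and at the upper end about 29 (59 against 30). The scheduling gap can be read directly from the text and is certain. The size of the gain is conditional on the assumed r and on the baseline being used as a covariate.

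**What to change.** In section 3, add a week-0 assessment, for example: CRS-R and GCS are scored before the allocation is revealed and before the first study treatment, on the same forms as at weeks 4, 6 and 8.

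In section 4:

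- name these week-0 scores as the before values, and list the measures and follow-up times that enter the before-and-after comparison;
- compare the arms on CRS-R and GCS at 4, 6 and 8 weeks by ANCOVA with the week-0 score of the same scale as covariate, not by a t-test on change scores.

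While section 3 is open, reconcile the two times given for GOS. A week-0 score would also document the starting state of a patient stopped before week 4, but it would not by itself justify carrying that value forward as the final result.

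The cost is one extra bedside assessment per patient (60 in total) on scales already in use, a few lines of text and slightly more analysis work. The plan does not say who scores CRS-R, so whether existing staff can absorb the extra assessment is for the sponsor to confirm.

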# Efficacy Observation of Electrical Stimulation of the Median Nerve Combined with Ear Acupressure on Consciousness Disorders in Patients with Cranial Brain Injury

## **1. Subject content and significance**

Consciousness disturbance after craniocerebral injury is a common neurosurgical emergency, which belongs to the category of "unconscious", "unconscious of people" and "confused" in traditional Chinese medicine. Patients often suffer from different degrees of consciousness disturbance due to damage of the reticular ascending activation system of the brain stem. The high mortality rate, high disability rate and high medical expenses of coma after craniocerebral injury brought great economic burden to the country, society and families, and also brought great life pressure and mental pressure to the family members.

Median nerve electrical stimulation (MNES) is a method of stimulating the median nerve with low-frequency pulse current, which stimulates the nervous system through the median nerve-spinal nerve-cervical spinal cord-brainstem-thalamus-cortical functional area conduction pathway. Electrical stimulation can relieve the inhibition of nerve cells, enhance the excitability of inhibited nerve cells, relieve the inhibition of the ascending reticular activating system (ARAS) in the brainstem, shorten the coma time of patients, and restore function, thereby promoting the recovery of consciousness.

Auricular acupressure is a new type of needle embedding method, has a high degree of safety and is easy to operate, and has achieved good clinical efficacy. And auricular acupuncture treatment, because of its close relationship with the z-fu organs and meridians, can play a good role in the "static and left" characteristics of the pressing needle, which can produce a continuous and stable stimulation after the is inserted under the skin, continuously promote the orderly circulation of qi and blood in the meridians, and stimulate the healthy qi of the human body, so as achieve the purpose of dispelling pathogenic factors. However, there are few reports on the promotion of auricular acupressure in the recovery of consciousness after craniocerebral injury. The purpose of this study was to apply median nerve electrical stimulation and auricular pressing needle to the treatment of consciousness disorders after craniocerebral injury, order to improve the effect of coma recovery in patients with craniocerebral injury.

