This study aims the common disturbance of consciousness in patients with head injury, combined with the application of median nerve electrical stimulation and auricular pressing needle therapy, to observe and analyze the efficacy difference between control group and the experimental group, with the purpose of accelerating the recovery of patients' consciousness, shortening the awakening time, and improving the effect of coma recovery in patients with injury, and to alleviate the economic pressure of society and families to the maximum extent.

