##### **1.3 Termination and handling of the trial**

In the course of the trial, those who have serious adverse events, or serious complications or worsening of the condition should be immediately removed from the clinical trial by the doctor. When the case is

stopped, the doctor should immediately give symptomatic clinical treatment. After the case is stopped, the doctor should investigate and record cause, retain the case observation data, and take the last detection result as the final result, and conduct data analysis on the efficacy and adverse reactions.

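### Awakening time is to be shortened, but the only method for measurement data is a t-test, which has no value for patients who never wake

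*Combined protocol and SAP*

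**What the plan says.** All references are to the combined protocol and SAP.

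- Section 3 (Research idea) lists "shortening the awakening time" among the aims.
- Section 3 (Observation indicators), item 3.1: "The time of patient awakening and the awakening at 4, 6, and 8 weeks after intervention were recorded".
- Section 4 (Statistical treatment) summarises measurement data as mean ± SD and adds: "Comparison within the group before and after treatment and comparison between the two groups were performed by t-test". For count data, a chi-square "test was used for the percentage or composition ratio between groups". It names no endpoint and has no survival method, censoring rule or rule for deaths.
- Section 1.3 covers patients removed for serious adverse events, serious complications or worsening: the doctor is to "take the last detection result as the final result".
- The plan expects some patients not to wake. Section 1 refers to "The high mortality rate, high disability rate and high medical expenses of coma after craniocerebral injury", and the outcome scale in item 3.4 includes the levels "2 indicates a vegetative state, and 1 indicates death".

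**The concern.** A t-test needs one number per patient. A patient still unconscious at 8 weeks, or who dies unconscious, has no awakening time, and no section says what to enter. That leaves two ways to run the test.

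1. **Drop patients without a time.** The comparison is then among patients selected by the outcome under study. An arm that wakes more people is compared only on how fast its awakeners woke, and the gain in numbers awake disappears from the analysis.
2. **Enter a value**, such as 8 weeks. Everyone stays in, but the plan gives no value, so it could be chosen after the data are seen.

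At stake is whether a reported mean awakening time can answer a question the trial set itself.

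**Working it through.** **Plan's own figure.** There is none to reproduce. The 60 patients come with no effect size, SD or expected awakening rate.

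**Step 1: what the plan supplies for each kind of patient**

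| Patient | Awakening time available? |
|---|---|
| Wakes within 8 weeks | Yes |
| Not awake at 8 weeks | No rule |
| Dies without waking | No rule |
| Removed while unconscious | Last result: a state or score, not a time |

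**Step 2: inputs for an illustration**

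- From the documents: 30 per group (section 1, Subjects), last awakening assessment at 8 weeks (section 3), significance at P<0.05 (section 4; two-sided is assumed, as sidedness is not stated).
- Assumed: the proportions awake by 8 weeks (control pC, experimental pE), constant hazards, and no deaths or removals. The 40% and 60% in background section 7 compare stimulation with a control group at no stated time. Both arms here receive stimulation, so those rates are not this trial's contrast.

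**Step 3: patients without a time.** Expected number = 30(1 − pC) + 30(1 − pE).

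- 40% vs 50%: 18 + 15 = 33 of 60
- 40% vs 60%: 18 + 12 = 30 of 60
- 60% vs 80%: 12 + 6 = 18 of 60

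Deaths or removals before waking would add to these.

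**Step 4: what each version of the t-test estimates.** With hazard λ = −ln(1 − p)/8, the mean time among awakeners is 1/λ − 8(1 − p)/p. With non-awakeners coded as 8 weeks, the mean is p/λ.

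| p | Mean, awakeners only (weeks) | Mean, non-awakeners coded 8 (weeks) |
|---|---|---|
| 0.4 | 3.66 | 6.26 |
| 0.5 | 3.54 | 5.77 |
| 0.6 | 3.40 | 5.24 |
| 0.8 | 2.97 | 3.98 |

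The same true benefit therefore appears as 0.12, 0.26 and 0.43 weeks among awakeners (40/50, 40/60, 60/80), but as about 0.5, 1.0 and 1.3 weeks when everyone is kept.

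**Step 5: power.** 20,000 simulated trials per scenario, 30 per arm, pooled-variance t, Pearson chi-square without continuity correction.

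| Awake by 8 weeks | t, awakeners only | t, coded 8 | 8-week chi-square | Log-rank |
|---|---|---|---|---|
| 40% vs 50% | 5.3% | 10.9% | 12.4% | 12.5% |
| 40% vs 60% | 6.2% | 30.3% | 34.8% | 35.3% |
| 60% vs 80% | 9.6% | 39.8% | 38.9% | 44.3% |

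Check at 40/60: the hazard ratio is ln(0.4)/ln(0.6) = 1.79 and 12 + 18 = 30 awakenings are expected. Schoenfeld's formula gives Φ(√30 × ln(1.79)/2 − 1.96) = 36%, in line with the simulated log-rank.

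**Step 6: errors.** In these three scenarios the awakeners-only t-test is significant in the wrong direction in 1.8%, 1.1% and 0.5% of trials. With no true effect (40/40 and 60/60), each t-test alone rejects in 4.9–5.2% of trials.

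**The case against.** **Section 4 never assigns the t-test to awakening time.** That stands: it is an inference from this being the only method for measurement data. If the inference is wrong, the stated purpose has no analysis at all, which needs the same repair. Nor does the plan say that non-awakeners will be dropped.

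**Awakening is already covered by chi-square at 4, 6 and 8 weeks.** Largely fair. Those comparisons need no awakening time and have nearly the power of log-rank, so a reader who inferred that awakening cannot be analysed would be wrong. They test status rather than time, however, and they keep every randomised patient only if deaths count as not awake, which is unstated.

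**One sentence fixing a code for non-awakeners would do.** It would remove the arbitrary choice, and the coded-8 t-test is within about 2 to 5 power points of log-rank. Log-rank is still preferable because it treats those times as censored rather than observed.

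**The time has an origin.** A reader might infer that it has none, since the entry criterion "Course of disease within 10 days" lets patients start at different points in their illness. Item 3.1 counts its assessments from the intervention, so start of intervention is a natural reading, though not explicit for the time variable.

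Three stronger inferences are tempting but unsupported:

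- *The two t-tests would often lead to conflicting conclusions.* Their mean differences do often differ in sign, but they do so in about 29–31% of trials even with no effect. That is mostly noise around a small awakeners-only difference, and rarely a significant conflict.
- *The false-positive rate is inflated.* It reaches about 9% only if the rule is chosen after seeing the data, by running both versions and reporting the smaller p-value. Nothing in the documents suggests that intention.
- *The better arm would look slower.* That needs the extra awakenings to come late, and the documents give no awakening-time pattern.

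**Conclusion.** The concern holds and should be fixed. The plan sets out to shorten awakening time but gives no usable analysis of it for patients who never wake, die first or are removed while unconscious.

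The main harm is that an awakeners-only t-test does not compare the randomised groups and has almost no ability to detect a real benefit: about 5–10% power, against 13–44% for log-rank in the same scenarios. Significant results in the wrong direction are rare, about 0.5–2%. The textual gap does not depend on any assumption. The power figures rest on assumed awakening rates, constant hazards and no deaths, and show scale only. The awakening comparisons at fixed weeks survive, which limits the damage.

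**What to change.** Add to section 4:

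> Time from randomisation to awakening is compared in all randomised patients with cumulative-incidence curves and a log-rank test. Patients not awake at 8 weeks are censored at 8 weeks; patients who die without waking are kept as not awakened to 8 weeks. No t-test is done on awakeners only.

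For this endpoint, supplement the last-result rule in section 1.3. Awakening and death continue to be recorded to 8 weeks in removed patients where possible. Otherwise they are censored at last assessment, with a sensitivity analysis counting them as not awakened to 8 weeks, because removal for worsening is informative. This concerns outcome recording only, not treatment.

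Keep the chi-square comparisons at 4, 6 and 8 weeks in all randomised patients, counting deaths as not awake.

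**Cost.** Slightly more analysis work in SPSS, recording of death dates, and outcome follow-up of removed patients. Keeping deaths to 8 weeks in an ordinary log-rank test is straightforward when all other censoring falls at 8 weeks. Patients censored earlier make it approximate, which is why follow-up and the sensitivity analysis matter. The power gain over the 8-week chi-square is small, about 0–5 points in the scenarios above, and could be a loss if extra awakenings come late. The change does not cure the low power of 30 per group.

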## **Ethics Batch Number (NTC): LLSL-2022053105**

### **4. Research Methods and Design**

#### **1. Subjects**

Sixty patients with head injury treated in our hospital were selected as subjects, randomly divided into control group and experimental, with 30 cases in each group.

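### Death has a value in GOS but none in GCS or CRS-R, so their mean comparisons either score a dead patient as living or leave a survivors-only comparison

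*Combined protocol and SAP*

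**What the plan says.** Section 3 (Observation indicators) lists GCS, CRS-R, GOS, awakening and family satisfaction, with comparisons after 4, 6 and 8 weeks. Item 3.2 gives GCS a maximum of 15 and states no minimum. Item 3.3 says of CRS-R: "lowest score is 0, and the highest score is 23. The higher the score, the higher the level of consciousness". Item 3.4 places GOS at one month after treatment and is the only item with a place for death: "2 indicates a vegetative state, and 1 indicates death".

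Section 4 (Statistical treatment) covers all score data in two sentences. "The measurement data of each group was expressed as mean ± standard deviation", and within-group and "comparison between the two groups were performed by t-test". The threshold is "P<0.05 was considered statistically significant", with sidedness not stated. No analysis set is defined, and no rule says how a death enters a score comparison.

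The only rule for incomplete cases is in section 1.3 (Termination and handling of the trial). A patient removed for a serious adverse event, serious complication or worsening keeps the last result obtained as the final result. Death is not named there.

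The sample is 60, "with 30 cases in each group", with GCS 4-8 at entry. Section 1 (Subject content and significance) refers to "The high mortality rate, high disability rate and high medical expenses of coma after craniocerebral injury" but gives no figure.

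**The concern.** A patient who dies before week 8 has no week-8 GCS or CRS-R, however complete the follow-up. The plan leaves two routes and does not say which applies.

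- **Through section 1.3.** A patient removed before dying keeps the last living score, so the analysis treats a death as a living patient at that level of consciousness.
- **Outside section 1.3.** Nothing is written, and a t-test on available scores uses survivors only. Survivors are selected after randomisation. If deaths fall mainly on patients with the poorest outlook, the arm with more deaths loses its lowest scorers and gains in mean score, while an arm that keeps severe patients alive is penalised.

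GCS and CRS-R measure the stated aim, recovery of consciousness, so an ambiguity here touches the main reading of the trial.

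**Working it through.** **What can be reproduced.** The plan gives no power, effect size, SD, mortality or dropout. Only 30 + 30 = 60 can be checked. Everything below is illustration under stated assumptions, using a two-sided 5% test (2.5% in each direction).

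**1. Fixed CRS-R example.** Both arms have the same 30 would-be week-8 scores, with mean 12.0 (sum 360) and SD about 5. The six lowest are 1, 4, 5, 6, 7 and 7 (sum 30, mean 5). These six patients die in one arm and nobody dies in the other. Differences are the higher-death arm minus the other.

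- Survivors only: (360 − 30)/24 − 12 = 13.75 − 12 = **+1.75**.
- Last score L carried forward: (330 + 6L)/30 − 12. For L = 2, 4, 6, 8 this gives **−0.60, −0.20, +0.20, +0.60**. The sign changes at L = 5, the mean those six patients would have reached.
- Death coded 0: 330/30 − 12 = **−1.00**.
- Death ranked below every living score: the probability that a patient in the higher-death arm does better is **0.480**, against 0.5 for no difference.

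**2. Closed form for the survivors-only gap.** Let the latent score be normal and let the lowest fraction p die. The survivor mean then rises by φ(z_p)/(1 − p) SDs, where z_p is the p-quantile of the standard normal and φ its density.

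- p = 0.05: 0.1031/0.95 = 0.109
- p = 0.10: 0.1755/0.90 = 0.195
- p = 0.20: 0.2800/0.80 = 0.350
- p = 0.30: 0.3477/0.70 = 0.497
- p = 0.40: 0.3863/0.60 = 0.644

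The gaps are 0.086 (5 v 10%), 0.155 (10 v 20%), 0.147 (20 v 30%) and 0.294 (20 v 40%). At an assumed SD of 4 GCS points they are about 0.3, 0.6, 0.6 and 1.2 points. Noise in who dies and the bounds of the scale reduce these somewhat.

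**3. Simulation, GCS-like score.** There are 30 per arm and severity z ~ N(0,1). A patient dies if z + 0.5 × noise falls below the quantile for the stated death rate. The score is 9.5 + 4z, rounded and held to 3-15 (the minimum of 3 is an assumption). Living-score distributions are identical in both arms.

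| Deaths, lower v higher arm | Survivors-only t-test, significant for the deadlier arm | Deaths ranked last, same direction |
|---|---|---|
| 20 v 20% | about 2.5% | about 2.3% |
| 5 v 10% | about 5% | – |
| 10 v 20% | about 8% | – |
| 20 v 30% | about 9% (runs 8.2-8.7%) | about 1% |
| 20 v 40% | about 20% (runs 18.2-20.6%) | 0.3-0.4% |

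The mean survivors-only difference is about 0.5 points at 20 v 30% and 1.0 at 20 v 40%. With a weaker link between death and score (noise SD 2), 20 v 40% gives +0.47 points and 6.5%.

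**4. Carry-forward in the same model.** Carrying an assumed entry score of 4-8 forward for deaths gives −0.16 points at 20 v 30% and −0.41 at 20 v 40%. Results significant for the deadlier arm fall to 1.6% and 0.9%. At the lower death rates the difference is close to zero.

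**5. Second model, CRS-R.** This assumes an early score of 5 (SD 2.5), a week-8 score of 12 (SD 5) and correlation 0.6. Death rates are 20, 30 and 40% against 10%.

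- Survivors only: +0.69, +1.34, +2.01 points; significant for the deadlier arm in 8.3%, 19.2%, 35.4%.
- Carry-forward: −0.36, −0.83, −1.41 points; 1.4%, 0.6%, 0.2%.
- Deaths ranked last, 30 v 10%: 0.7%.
- Equal deaths, 10 v 10%: no bias.

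**The case against.** A reader might infer that the plan specifies a survivors-only analysis, so that a harmful treatment would come out looking effective. The documents do not support that. No passage prescribes a survivors-only analysis; it is what remains for deaths that section 1.3 does not catch. The written rule is carry-forward, and many deaths in this population would be preceded by a serious adverse event or worsening and so pass through it. Under that rule the reversal does not appear on average. It arises only when the last living scores exceed what those patients would later have scored. For the same reason the point cannot be held wholly separate from section 1.3, because the last-score half of it is that rule applied to deaths.

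The death rates are also open to challenge. The remark about high mortality concerns coma after craniocerebral injury in general. This trial requires stable vital signs and no severe organ failure, and excludes other critical illness. The arms share conventional care and median nerve stimulation and differ by the auricular component, which the plan regards as safe. A 10 to 20 point excess of deaths is therefore a severe scenario, and the 5 v 10% row belongs beside it.

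Worst-rank scoring is one option among several, and it changes the question to a composite of death and consciousness.

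These points limit the size and direction of the problem. They do not supply the missing rule: the plan still does not say how a death enters the GCS and CRS-R comparisons.

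**Conclusion.** The gap is real and should be closed. Followed as written, the plan either gives a dead patient a living score or drops that patient, and it does not say which.

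The two routes differ in consequence. Carry-forward mainly understates harm. Survivors-only means can favour the deadlier arm: wrong-direction significance rises from the nominal 2.5% to about 5% at 5 v 10% deaths and about 20% at 20 v 40%.

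Those figures rest on assumed death rates, an assumed score distribution and deaths concentrated in severe patients. They shrink when death is weakly linked to the score, and they vanish when deaths are equal in number and kind. They show what the silence allows and do not predict this trial's result.

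**What to change.** Add to section 4:

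- Record the date of death for every randomised patient, including those removed under section 1.3. GOS at one month after treatment does not give vital status at each visit.
- At 4, 6 and 8 weeks, rank a patient known to have died below the lowest living GCS or CRS-R score, and compare all 60 randomised patients by rank-sum test. Do not code death as 0, which would tie with a living CRS-R of 0.
- State that the last-result rule in section 1.3 does not supply GCS or CRS-R scores for patients who have died.
- Count a patient who died without awakening as not awakened, with 30 per arm as the denominator.
- Print deaths by arm beside each GCS and CRS-R result, and label survivor-only means as descriptive.

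The cost is a few sentences and one date field. The downside is that the main GCS and CRS-R results become rank comparisons that include death, and the difference in points becomes secondary. Missing scores in living patients are not addressed by this change and still need their own rule.
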